Currently at TriHealth, Inc. all implanted port catheters are flushed according to the TriHealth Nursing Policy and Procedure Intravenous Site Guidelines (See Appendix A). An implanted port catheter is flushed with normal saline after IV medication, blood, or blood draws. Heparinized saline in the amount of 5 mL (concentration 100 units/mL) is used as a final flush when no IV fluids are running and before de-accessing. This is intended to maintain patency of the catheter until the next use. The same process is used at University of Cincinnati Medical Center Barrett Infusion Center, a new site added to the study in January 2018.

TriHealth wide, there is no accurate data describing either the number of port catheters that are in use or the specifics of the complication rate. This data also is lacking UCMC wide. During the period of time between May 2, 2011 and April 30, 2012, the Out-Patient Cancer Care (OPCC) at TriHealth, utilized 134 doses of alteplase (Cath-Flo) to resolve occlusions. There is no easily accessible data describing whether these were partial (flushable but without a blood return) or complete (unable to flush) occlusions. There is no easily accessible information summarizing the type of central line that had to be de-clotted; however, the majority (>95%) of central lines

utilized by cancer patients in the OPCC are single lumen implanted port catheters. During this time period, there were two patients receiving care in the OPCC whose catheters were not flushed with a heparinized saline solution. One patient has documented HIT, and the other has a reported heparin allergy. Both patients have been able to maintain patent catheters with saline only flushes. Hospital wide, information related to the diagnosis of HIT, as it relates to type of Heparin exposure (e.g., subcutaneous or IV Heparin or the use of heparinized saline) is not available. There are no data available that demonstrates that patients with implanted port catheters who have developed a partial or complete occlusion developed bacteremia or central line infection due to the presence of fibrin on their catheter. Development of a fibrin sheath on the catheter is common after placement of an implanted port catheter (Gallieni, Pittiruti, & Biffi, 2008). The fibrin sheath may then become seeded with microorganisms which may disseminate into the blood stream. Both catheter-related thrombus and bacteremia are potentially life-threatening conditions.

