Based on the literature and our own experience we estimated an approximate occlusion rate of 20% with the standard treatment (saline + heparinized saline flush as described above). The power analysis conducted by [name] determined that, using a two-group normal approximation test of proportions with a one-sided .05 significance level, a sample size of 198 participants per group will have 80% power to reject the null hypothesis that the proposed method is not inferior (i.e. the difference in proportions between the proposed method and the standard method is greater than 0.10). Thus, we will continue data collection until 198 have been completed in each group for a total of 396 study participants who completed 6 months of data collection. To date (July 3, 2019), 69.7% of patients enrolled in the study are able to complete 6 months of data collection without withdrawing for an exclusion criterion (ex: transferring to hospice, being started on an anticoagulant, etc). Therefore, we plan to consent 575 patients to result in 396 who complete the study. Once 396 patients have completed 6 months of data collection will stop and any remaining active participants will be withdrawn from the study.

Data Collection:

Independent Variables: Method for flushing implanted port catheters:

• 20 mL of saline followed by 5 mL of Heparinized saline in a concentration of 100 units/mL

OR

• 20 mL of saline only

Dependent Variables:

Primary Outcomes

- Occurrence of first complete (can neither withdraw blood nor flush the catheter) occlusion
- Occurrence of first partial (able to flush but unable to withdraw blood) occlusion
- Frequency with which alteplase (CathFlo) has to be utilized to resolve an occlusion

Secondary Outcomes

- Number of subsequent occurrences of complete or partial occlusions after the first occurrence.
- Amount of time in days that a port remains patent (flushes easily and able to obtain a blood return).
 - Amount of time between entrance in study and first incidence of partial or complete occlusion
 - Amount of time between incidences of partial or complete occlusion.
- Occurrence of other complications:
 - Central Line-Associated Blood Stream Infection (CLABSI) a laboratory-confirmed (recognized pathogen cultured from one or more blood cultures; organism cultured from blood is not related to an infection at another site) blood stream infection that is considered central line associated (CDC, 2012).
 - Develops complication related to Heparin

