Potential risks for study participants in either arm of the study include partial occlusion (can instill flush solution but not withdraw blood) and complete occlusion (can neither instill flush solution nor withdraw blood). Study participants could require removal of the port if an occlusion cannot be resolved, and possibly require re-insertion of a new implanted port. In the event of any occlusion, alteplase (CathFlo) in the policy established dose and frequency (see Appendix A) will be instilled to resolve the occlusion. Study participants whose implanted ports are found occluded on three (3) consecutive visits to the treatment center will be excluded from further data collection, i.e., their participation in the study will be terminated. The standard flushing as prescribed by the site's policy or as prescribed by the attending physician will be used. Study participants whose occlusion cannot be resolved with alteplase and require removal of the port will also be terminated and excluded from further data collection. Patients who develop port infections necessitating port removal will be terminated and excluded from further data collection. Study participants who develop HIT (heparin induced thrombocytopenia) or other heparin allergy will be terminated and excluded from further data collection. Likewise, patients who have thrombotic or embolic phenomenon requiring therapeutic anticoagulation will be terminated and excluded from further data collection. If a participant in the intervention group receives clinical care and their port is flushed with heparin (following standard hospital policy), the participant will be withdrawn from the study.

The study will be closed if there is evidence that study participants in the intervention arm experience implanted port occlusion at a disproportionate rate. The amount of alteplase (CathFlo) used in each group will be assessed each

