month for monitoring purposes. Additionally interim data analysis will occur (1) once 1/3 of the participants have been enrolled in each group; (2) once 2/3 of the participants have been enrolled in each group (3) at the conclusion of the study. These intervals are based on the recommendation of our CCTST consultant [name]. The variable of interest in the interim data analysis at time (1) and (2) will be the occurrence of first partial occlusion plus the occurrence of the first complete occlusion in each group. At final analysis the occurrence of first partial occlusion and first complete occlusion will be considered together as well as separately in each group. [name] also advised that to control for the Type I error rate not to exceed the nominal .05 level, the p-value should be adjusted at each data interim analysis. [name] used the O'Brien Fleming alpha spending method to calculate the alpha levels for each interim analysis (O'Brien & Fleming, 1979). Thus, in order to reject the null hypothesis that the proposed procedure will produce a failure rate greater than 10% over the occlusion rate experienced using the standard procedure, the p-value at the 1st, 2nd and final analysis should be compared with an alpha value of 0.0006, 0.0151 and 0.0471 respectively. Thus if, using the p-values noted, interim calculations at time (1) or time (2) note a significant increase in the occlusion rate among participants in the intervention group, the study will be prematurely closed.

The undertaking of this research does require the participation of other personnel, facilities or departments other than those used in data collection. In the event the study participant is admitted to the hospital or requires some intervention using their implanted port catheter (e.g., CT scan with contrast), the study participant will have an information card describing his/her participation in the study and the group to which he/she has been randomized, so that the assigned flush solution is used, and integrity of the study can be maintained. The study participant will receive the card with instructions at the time of his/her enrollment in the study (see Appendix E Wallet Study Card).

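### Monitoring by arm and the closure rules cover only occlusion and alteplase; infection and heparin reactions have no interim comparison, and thrombotic or embolic events have no planned comparison at any time

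*Combined protocol and SAP*

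**What the plan says.** Monitoring and closure are set out under Experimental Aspect of the Study. The general closure rule is: "The study will be closed if there is evidence that study participants in the intervention arm experience implanted port occlusion at a disproportionate rate". For the routine check, "The amount of alteplase (CathFlo) used in each group will be assessed each" month. Two interim analyses follow, the first "once 1/3 of the participants have been enrolled in each group" and the second at two thirds. "The variable of interest in the interim data analysis at time (1) and (2) will be the occurrence of first partial occlusion plus" first complete occlusion. The interim rule is that if these calculations "note a significant increase in the occlusion rate among participants in the intervention group, the study will be prematurely closed".

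Other harms appear elsewhere. Under Data Collection, Secondary Outcomes, the plan lists CLABSI, HIT and other heparin allergy. The Statistical Analysis section compares the dependent variables between groups but gives the secondary outcomes no interim timing. Experimental Aspect of the Study ends an individual's participation for port infection leading to removal, for HIT or heparin allergy, and for thrombotic or embolic events that need therapeutic anticoagulation. The last of these is not among the primary or secondary outcomes.

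The Background (Care of Implanted Port Catheters at TriHealth) describes how a fibrin sheath can be seeded with organisms and adds: "Both catheter-related thrombus and bacteremia are potentially life-threatening conditions".

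**The concern.** The trial withholds heparin from one arm, and part of its stated purpose is to find the safest flush. Research question 2 asks whether the type and rate of complications differ by arm. The event being monitored, occlusion, is the frequent one, and the plan has a routine treatment for it. The events that the Background treats as most serious are recorded and acted on one participant at a time, but nobody is instructed to set them side by side by arm while the trial is running.

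If the saline arm had more bloodstream infections or more thrombosis needing anticoagulation, without more occlusions, every planned check would be passed and enrolment would continue. For thrombosis the gap lasts beyond the trial, because the planned end-of-study comparisons cover only listed outcomes.

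**Working it through.** **1. Each event against each safeguard in the text.**

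| Event | Monthly check | Looks 1 and 2 | Closure trigger | Comparison at the end | Action for the individual |
|---|---|---|---|---|---|
| Partial or complete occlusion | Yes, through alteplase amount | Yes | Yes | Yes | Terminated if repeated or if the port must be removed |
| CLABSI | No | No | No | Yes, secondary outcome | Terminated if port infection leads to removal |
| HIT or other heparin allergy | No | No | No | Yes, secondary outcome | Terminated |
| Port infection leading to removal | No | No | No | Only if it also meets the CLABSI definition | Terminated |
| Thrombotic or embolic event needing anticoagulation | No | No | No | Not specified | Terminated |

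Only the first row has any comparison by arm before the end. The last row has none at all.

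**2. Is occlusion an adequate stand-in?** The Purpose section names thrombus as the main cause of occlusion, so occlusion and alteplase use carry some information about thrombus in or around the catheter. They do not count bloodstream infections, and they do not count thrombosis serious enough to need anticoagulation.

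**3. The plan's own sizes.** The Recruitment section gives a 20% occlusion rate, a margin of 0.10, one-sided 0.05 and 80% power. With the unpooled normal approximation, n = (1.645 + 0.842)² × 2 × 0.20 × 0.80 / 0.10² ≈ 198 per group, as stated. For consents, 396 / 0.697 gives 569, close to the stated 575. All of this concerns occlusion; nothing is sized for other harms.

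**4. Who is still to enrol after look 2.** The text does not say whether the fractions refer to the 198 per group or to the 575 consents.
- Base 198: look 1 at 198/3 = 66 per arm and look 2 at 132 per arm. Then 575 − 2 × 132 = 311 consents remain.
- Base 575: look 1 at about 96 per arm and look 2 at about 192 per arm. Then 575/3 ≈ 192 consents remain.

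**5. What a formal test could detect.** The documents give no infection or thrombosis rate, so the rates below are assumptions. The table shows the chance that a one-sided Fisher test at 0.05 flags the excess.

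| Control v saline | 66 per arm | 132 per arm | 198 per arm |
|---|---|---|---|
| 1% v 3% | 3% | 14% | 26% |
| 2% v 6% | 14% | 37% | 57% |
| 3% v 9% | 28% | 57% | 77% |
| 2% v 8% | 30% | 64% | 84% |

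At 2% v 6% the expected counts are 66 × 0.02 = 1.3 and 66 × 0.06 = 4.0 at look 1 on base 198, and 132 × 0.02 = 2.6 and 132 × 0.06 = 7.9 at look 2. On base 575, look 2 would have 192 × 0.02 = 3.8 and 192 × 0.06 = 11.5. These are upper figures. The looks are timed by enrolment, so many participants would not yet have six months of follow-up. The counts can inform judgement, but they are too few for a useful boundary.

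**The case against.** The strongest case against has four parts.

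- **Pathway.** The only mechanism the Background offers for infection runs through fibrin, and thrombus is also the main cause of occlusion, so occlusion is an earlier and more frequent signal on the same path. This stands in part: it limits the gap for catheter thrombus but not for infection or for thrombosis needing anticoagulation.
- **Sparse data.** Early comparisons would often miss a real excess and could raise chance alarms. This stands against a formal test, though not against a descriptive table.
- **Other protection.** Affected participants are withdrawn, the study had full-board ethics review, and the appendices and consent form were not available here. Adverse-event reporting described only there cannot be ruled out. Withdrawal of individuals is nevertheless not a comparison of arms, and the section that sets out monitoring and closure names only occlusion and alteplase.
- **Workload.** Records are on paper. Complications go on the Face Sheet, which stays in the patient's folder; forms from the added site come back only periodically; and data entry is described as following study completion. This stands against a monthly table.

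A reader might infer that saline-only flushing is likely to cause more infection or thrombosis. The documents do not support that. The Background says there are no data showing that patients with occluded ports went on to line infection because of fibrin, and some area hospitals already flush with saline only. A reader might also infer that the trial ignores these harms. It does not: it records them, acts on individuals, and plans an end-of-study comparison for CLABSI and heparin reactions.

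**Conclusion.** The point holds as a gap in what is watched by arm, and it is worth correcting. All planned comparisons before the end, and both closure triggers, concern occlusion or its treatment. CLABSI and heparin reactions wait until the final analysis, and thrombotic or embolic events are not compared by arm at any time.

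The size cannot be given as an expected number of harms, because the documents contain no infection or thrombosis rates. What can be stated is the exposure: about 311 consents still to come after look 2 if the fractions refer to 198 per group, or about 192 if they refer to the 575 consents. The conclusion assumes that the unavailable appendices contain no safety comparison by arm. It does not assume that an excess is likely, and it does not affect the alpha levels planned for occlusion.

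**What to change.** Make three changes.

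1. **Interim analyses (Experimental Aspect of the Study).** At looks 1 and 2, add a descriptive table by arm of CLABSI, terminations for thrombotic or embolic events, port removals for infection, and HIT or other heparin reactions, each with participant-time. Count every randomised participant, including those terminated, because people with these terminating events cannot be among the completers. Specify no formal test and no alpha boundary.
2. **Closure paragraph (same section).** State that a marked imbalance in these events, in either direction, is grounds for reviewing whether the study continues, and name the role responsible for that review. No numerical trigger is needed.
3. **Secondary Outcomes.** List thrombotic or embolic events needing therapeutic anticoagulation as an outcome, compared by arm at the end.

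The events are already recorded, so no new measurement is required. The cost is collecting and collating Face Sheets from all sites at each of the two looks and calculating follow-up time. The downside is that small counts can show chance imbalances. The text should say so, so that a difference of a few cases is read as a prompt for review and not as a finding.

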Statistical Analysis: Descriptive statistics will be used to describe the participants. Differences between groups on the dependent variables will be calculated using t-test, Chi-Square or Fisher's exact test as appropriate for the level of data under analysis (also see discussion regarding interim analysis). Regression analysis will be used to determine the effect of the moderating variables on the occurrence of occlusion in the implanted ports. Participants in the control group and intervention group will be further stratified based on frequency of port flushing. Differences in the rate of occlusion between stratified groups will also be calculated.

Ethical Considerations: The purpose of this study is to determine the safest and most effective flushing solution(s) for maintaining patency in implanted port catheters. In so doing, study participants could be placed at potential risk for catheter occlusion. All catheter occlusion will be treated according to the site's policy, i.e., the instillation of alteplase (CathFlo) (see Appendix A). Potential study participants will be made aware of

the risk when enrolled in the study (See Appendix B (V.2, 2-20-2015) script for recruiting patients into the study and Appendix F, the Informed Consent Statement).

- **Informed Consent:** Patients who meet inclusion criteria will be approached by a member of the research team who will explain the study, implications of their participation and review the Informed Consent Statement and HIPAA Authorization Form(s) (see Appendix F and G). Participants will receive a copy of the signed Informed Consent Statement and HIPAA Authorization. The original signed Informed Consent Statement and HIPAA will be stored in a locked cabinet at a TriHealth office or locked location at UCMC, or an off-site locked storage area, for six years after the study is closed at which time the documents will be destroyed via mechanical shredder.

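### The interim levels have the shape of a two-sided .05 O'Brien-Fleming boundary but serve a one-sided .05 non-inferiority design; if interim looks can reject inferiority, neither sidedness gives the stated error and power

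*Combined protocol and SAP*

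**What the plan says.** The sample-size paragraph (under Recruitment) assumes about 20% occlusion on standard flushing and a margin of 0.10. It specifies a "two-group normal approximation test of proportions with a one-sided .05 significance level, a sample size of 198 participants per group will have 80% power". On duration it says: "Once 396 patients have completed 6 months of data collection will stop".

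The interim paragraph (under Experimental Aspect of the Study) places looks at 1/3 and 2/3 of enrolment in each group and at the end. It says the p-values are adjusted "to control for the Type I error rate not to exceed the nominal .05 level" and cites O'Brien-Fleming alpha spending. It gives the purpose of the levels as "in order to reject the null hypothesis that the proposed procedure will produce a failure rate greater than 10% over the occlusion rate" seen with the standard procedure, and says that the p-value at the three analyses "should be compared with an alpha value of 0.0006, 0.0151 and 0.0471 respectively".

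The next sentence uses the same p-values for something else: if the first or second look should "note a significant increase in the occlusion rate among participants in the intervention group, the study will be prematurely closed". The preceding paragraph has a general form of this rule: "The study will be closed if there is evidence that study participants in the intervention arm experience implanted port occlusion at a disproportionate rate".

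The Statistical Analysis section lists the t-test, Chi-Square and Fisher's exact test, "as appropriate for the level of data under analysis (also see discussion regarding interim analysis").

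**The concern.** Two things do not fit together.

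First, the interim paragraph never says whether its p-values are one- or two-sided. The design is one-sided, yet the levels have the O'Brien-Fleming shape only when read as two-sided. Depending on the reading, either the promised error limit is slightly exceeded or the power is well below the stated 80%.

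Second, one sentence attaches the levels to rejecting inferiority, a result in favour of saline. The next attaches them to closing the study because saline does worse. The plan does not say what follows if inferiority is rejected at a look, or which difference an increase in occlusion is measured against. At stake are the level at which the final claim is judged and how readily the participant-protection rule would act.

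**Working it through.** **Inputs.** Control rate 20%, margin 0.10, one-sided .05, 80% power and 198 per group come from the sample-size paragraph. Levels 0.0006, 0.0151 and 0.0471 and looks at 1/3, 2/3 and the end come from the interim paragraph. Assumptions: equal true rates for power, and information fractions t = 1/3, 2/3, 1.

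**1. Reproduce the sample size.** n = (1.645 + 0.842)² × 2(0.2)(0.8) / 0.10² = 197.8, hence 198. The figure reproduces as a single-analysis number with no allowance for looks. The drift (expected final z with equal arms) is 0.10 / √(0.32/198) = 2.487.

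**2. Shape of the levels.** An O'Brien-Fleming boundary has constant z × √t.

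| Reading | z at looks 1, 2, final | z × √t |
|---|---|---|
| One-sided | 3.239, 2.167, 1.674 | 1.87, 1.77, 1.67 |
| Two-sided | 3.432, 2.430, 1.985 | 1.981, 1.984, 1.985 |

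Only the two-sided reading is constant. An exact two-sided .05 boundary has constant 2.004, so the printed one is slightly loose (0.0524 over both tails).

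**3. Error and power.** The z statistics are jointly normal with correlation √(tᵢ/tⱼ); I take the probability of crossing at any look.

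| Reading | Non-inferiority type I error | Power |
|---|---|---|
| One-sided, any look can reject inferiority | 0.0006 + 0.0147 + 0.0361 = 0.0514 | 79.8% |
| Two-sided, any look can reject inferiority | 0.0262 | 70.0% |
| One-sided, looks only close for excess occlusion | at most 0.0471 | at most Φ(2.487 − 1.674) = 79.2% |

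Rounding of the printed levels moves the first error only between 0.0513 and 0.0515.

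**4. Repair.** Keeping 0.0006 and 0.0151 and solving for the final level at one-sided .05 gives z = 1.689, level 0.0456: error 0.0500, power 79.4%. Restoring 80% would need 201.4, that is 202, per group.

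**5. Sensitivity to timing.** Looks are set by enrolment, but the 198 counts six-month completers, so interim information may be below 1/3 and 2/3. At assumed fractions (0.25, 0.60) the one-sided error is 0.0525 and the final level would be 0.0444. At (0.10, 0.40) they are 0.0556 and 0.0410.

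**6. Direction.** With equal arms and one-sided p-values, inferiority is rejected with probability 3.6% at look 1 and 44.7% by look 2. The chance of closing for excess occlusion by look 2 (control 20%, one-sided) is:

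| True saline rate | Against zero difference | Against 10 points |
|---|---|---|
| 20% | 1.5% | about 0% |
| 30% | 39% | 1.5% |
| 40% | 93% | 36% |

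**The case against.** The best counter-argument is that 0.0514 rests on two things the interim paragraph leaves open. If the levels are two-sided, as their shape suggests, the error is 0.026 and the .05 promise is kept. If the looks serve only as a harm check, non-inferiority is tested once, at 0.0471. The only interim action the plan states is closure for excess occlusion, and collection otherwise runs to 396 completers. Both points stand, so the error excess can only be stated conditionally. Neither removes the problem. The two-sided reading costs about ten points of power. The harm-only reading conflicts with the sentence that ties the first and second levels to rejecting inferiority.

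The excess is also tiny: 0.0514 − 0.05 = 0.0014, about the size of the error in the normal approximation. Binomial simulation at 30% against 20% gives about 0.052 with the printed levels and just over 0.050 with the lowered final level. That stands too. Uncertainty about the true rate matters more: at 15% to 25% in both arms (an assumed range), one-sided power runs from 87.1% to 74.1%.

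Finally, the Statistical Analysis section points to the interim discussion, so an ordinary Chi-Square or Fisher comparison with zero difference is a natural reading of the closure rule. That is fair, but the pointer does not assign a test, and the null just stated in the interim paragraph uses 10 points.

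**Conclusion.** The point holds as a minor one. Levels with a two-sided shape are attached to a one-sided fixed-sample design. If the looks can reject inferiority, neither sidedness yields one-sided .05 with 80% power: the result is 0.0514 with 79.8%, or 0.026 with about 70%. These figures assume a 0.10 margin, 198 per group, information of 1/3, 2/3 and 1, and 20% occlusion in both arms for power.

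A reader might infer that the trial's type I error simply exceeds .05. The documents do not support that without conditions, because they state neither the sidedness nor whether an interim rejection counts. A reader might also infer that the closure rule is wholly unspecified. It is not: a list of tests and a cross-reference exist, and what is missing is mainly clarification. Even so, the two interim sentences do use one set of levels in opposite directions, and they need to be reconciled with each other and with the stop at 396 completers.

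**What to change.** - State that the non-inferiority p-values are one-sided against the 10-point margin.
- Keep 0.0006 and 0.0151, since looks may already have taken place (the documents do not say). Lower the final level to about 0.0456, recomputed at the actual information fractions and fixed before the final data are seen.
- Restate power as about 79%, or about 70% if the levels are kept as two-sided.
- Say whether an interim rejection of inferiority counts as the trial's result and what follows it, consistently with the stop at 396 completers. If the looks are meant only for closure, say so; the final 0.0471 then stays within .05.
- State the excess-occlusion comparison in its own sentence, with its test, reference difference, sidedness and level, and align it with the general closure sentence. The choice of reference difference is for the study team.

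The cost is a few sentences, one level and one power figure, with no added patients. The downside is about 1 point of stated power (79.4% against 80%). Recovering it would take 202 instead of 198 per group, 4 more per group.

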Participants in the control group will have their implanted port catheters flushed according to the established site's policy. Following the use of the port catheter with no continuous fluids running, or before de-accessing a port catheter (removing the port needle), the port will be flushed with 20 ml of normal saline and 5 ml of heparinized saline in the concentration of 100 units of heparin per ml.

Participants in the intervention group will have their ports flushed with normal saline only. That is, following the use of the port catheter with no continuous fluids running, or before de-accessing a port catheter (removing the port needle), the port will be flushed with 20 ml of normal saline. Turbulent flushing technique (the solution is injected using a push/pause technique every 1 mL) will be used in both groups and all accessed port catheters will have a neutral displacement connector. The MicroCLAVE[®] Clear displacement connector (ICU Medical, Inc., San Clemente, CA, USA) is the current product in use. Participants in both groups will be seen in a TriHealth Cancer Institute Infusion Center or the UCMC Barrett Infusion Center at a frequency consistent with their individual treatment plan and as outlined in the site's policy. Participants will remain in the study for 6 months or until they experience one of the potential risks noted below. Participants will be considered as having completed the study if they participate for 6 months.

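### The interim levels are set for rejecting inferiority, then reused to close the trial for excess occlusion on saline, with no null or sidedness stated for that second test

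*Combined protocol and SAP*

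**What the plan says.** All of the interim plan is in the protocol's Experimental Aspect of the Study section.

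- **Purpose of the levels.** P-values are adjusted "to control for the Type I error rate not to exceed the nominal .05 level". Then, "in order to reject the null hypothesis that the proposed procedure will produce a failure rate greater than 10% over the occlusion rate" seen with the standard flush, "the p-value at the 1st, 2nd and final analysis should be compared with an alpha value of 0.0006, 0.0151 and 0.0471 respectively".
- **Action at the looks.** The following sentence says that if, at those p-values, looks 1 or 2 "note a significant increase in the occlusion rate among participants in the intervention group, the study will be prematurely closed". No other interim action is given.
- **General closure clause.** "The study will be closed if there is evidence that study participants in the intervention arm experience implanted port occlusion at a disproportionate rate". No threshold is attached. Alteplase use by group is also reviewed monthly.
- **Timing.** Look 1 comes "once 1/3 of the participants have been enrolled in each group" and look 2 at two thirds. Completion is defined separately: "Participants will be considered as having completed the study if they participate for 6 months".

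Elsewhere, the Null Hypothesis section defines one null, the 10-point margin. The power paragraph (under Recruitment) plans a one-sided .05 test with 198 per group, and says data collection continues until 198 per group have completed. Statistical Analysis names the t-test, chi-square or Fisher's "exact test as appropriate for the level of data under analysis (also see discussion regarding interim analysis"), without a null or sidedness.

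**The concern.** Two consecutive sentences give one set of p-values opposite meanings. In the first, crossing a level means that saline has been shown to be less than 10 points worse. In the second, it means that saline is worse and the trial closes. Rejecting the only null in the document cannot show an increase on saline, so the closure rule needs a second null, and none is written.

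This is the trial's only quantified rule for closing on excess occlusion, and the null that the reader supplies decides how protective it is. The same gap leaves two other questions open: whether a look that crosses a level in saline's favour allows a non-inferiority claim, and whether the levels apply to one-sided or two-sided p-values. The answers decide whether the stated .05 cap is met.

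**Working it through.** **Inputs.** Heparin rate 20%, margin 0.10, one-sided .05, 80% power and 198 per group (power paragraph). Levels 0.0006, 0.0151, 0.0471, with looks at 1/3 and 2/3 (Experimental Aspect). Complete data at those looks would be 66 and 132 per group.

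**1. Direction.** Let d be the saline minus heparin occlusion rate.
- Non-inferiority: z = (0.10 − d)/SE. Large values favour saline.
- Harm against zero: z = d/SE.
- Harm against the margin: z = (d − 0.10)/SE, the non-inferiority statistic with its sign reversed.

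**2. Sample size.** n = 2(0.2)(0.8)(1.645 + 0.842)²/0.10² ≈ 198, as stated. The standardised effect is 0.10/√(0.32/198) = 2.487. Power is Φ(2.487 − 1.645) = 0.800.

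**3. Where the levels come from.** Read as two-sided p-values, their z-values are 3.432, 2.430 and 1.985. The ratios to the last are 1.728 and 1.224, which match O'Brien-Fleming (√3 = 1.732, √1.5 = 1.225). The single constant 1.985 gives 0.00059, 0.01505 and 0.04714, which round to the listed levels. Holding two-sided .05 needs 2.004, which gives 0.0005, 0.0141 and 0.0451. Read as one-sided, the z-values are 3.239, 2.167 and 1.674, with ratios 1.935 and 1.295, which is not that shape.

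**4. Overall error if non-inferiority may be claimed at any look.** This is the probability that a trivariate normal, with correlations √(tᵢ/tⱼ), crosses at least one boundary.

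| Information at looks 1, 2, 3 | One-sided p | Two-sided p |
|---|---|---|
| 1/3, 2/3, 1 | 0.0514 | 0.0524 |
| 70% and 85% of the planned interim information (assumed) | 0.0530 | 0.0542 |
| Half of it at both looks (assumed, severe) | 0.0564 | 0.0576 |

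The last two rows are illustrations, because looks are triggered by enrolment while completion takes six months. In the first row, power with one-sided p-values is 79.8%. With two-sided p-values, the error in the non-inferiority direction alone is 0.026 and power is 70%, but the power paragraph does not plan that.

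**5. Error if looks can close only for harm.** Non-inferiority is then tested once at 0.0471, which is under .05. Power is Φ(2.487 − 1.674) = 0.792 against 0.800 at .05, so the reduction costs under one point and is not needed.

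**6. What the choice of null does to closure.** Take heparin at 26/132 at look 2. One-sided z must exceed 2.167 and two-sided 2.430.
- Against zero (pooled z): saline 42/132 gives 0.1212/0.0538 = 2.25, while 41 gives 2.12. Closure starts at 42 one-sided, or 44 two-sided (2.51).
- Against the margin (unpooled z): 55/132 gives (0.2197 − 0.10)/0.0551 = 2.171, while 54 gives 2.04. Closure starts at 55 one-sided, or 57 two-sided (2.44).

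Probability of closure by look 2, heparin at 20%, 1,000,000 simulated trials per case, full information, two-sided to one-sided p-values:

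| True saline rate | Null of zero | Null of +10 points |
|---|---|---|
| 40% | 88–92% (Fisher 85–90%) | 28–37% |
| 20% | 0.8–1.5% (Fisher 0.5–1.0%) | near 0 |

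**7. How often the unstated claim would arise.** With equal true rates of 20%, the levels are crossed in saline's favour by look 2 in 35–45% of trials at full information.

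**8. Levels that hold one-sided .05.** The O'Brien-Fleming constant is 1.7096, giving 0.0015, 0.0181 and 0.0437. Error is 0.0500 and power 79.1%. At half information at both looks, even these give 0.0557.

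**The case against.** The strongest reply is that the plan can be run as it stands. A significant increase on saline ordinarily means a test against zero, the Statistical Analysis section names tests that do this and points to the interim discussion, and the rule then performs well. Reading it against the margin is strained, and monthly alteplase review adds a further safeguard. This stands. A reader might infer that the trial has no workable harm rule, and the documents do not support that. What remains is that the null must be inferred, against the only one defined and against the sentence just before.

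A reader might also infer that the plan inflates type I error above .05. That is not established. The excess arises only if non-inferiority may be claimed at looks 1 and 2. The instruction to continue to 198 completers per group, with harm as the only stated interim action, suggests that looks do not stop the trial for non-inferiority. It does not say whether a claim may be made while the trial continues.

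Finally, the size of any information shortfall is unknown. Slow accrual would leave most enrolled participants complete at each look, and occlusions before six months already count. Half information at both looks is a severe case, not an estimate.

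**Conclusion.** The concern holds as a defect in a stated decision rule: the levels are tied to one null and then used to act in the opposite direction, with no null or sidedness given for that use. It should be corrected, because with heparin at 26/132 at look 2, any saline count from 44 up to 54 closes the trial against zero and does not close it against the margin, whichever sidedness is used.

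The effect on error is small and conditional. If early claims are allowed, error is 0.0514 or 0.0524 at the planned information, and about 0.053 to 0.058 in the reduced-information cases shown. If looks are for harm only, the cap holds and 0.0471 is stricter than it need be. The figures assume a 20% heparin rate, equal groups and 198 completers per group.

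**What to change.** Reconcile the two sentences by writing two separate rules.

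- **Harm.** State a null of zero difference, the test statistic and the sidedness. The sponsor and its statistician choose the boundary. Say how the clause on a disproportionate occlusion rate relates to it.
- **Non-inferiority.** Either state that looks 1 and 2 cannot claim it and test once at one-sided .05 (power about 80%), or keep early claims, say whether the trial then stops, and use one-sided levels 0.0015, 0.0181 and 0.0437 with power restated as about 79%. In the second case, recompute the levels from the information actually available at each look.
- **Looks already done.** The document does not say whether any has taken place. If one has, change the remaining levels only if that look tested non-inferiority, using the actual information, and document this in an amendment.

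The cost is one paragraph and one recalculation, plus about one point of stated power if early claims are kept. There is also a trade-off to accept openly. A harm test against zero can close a trial whose true difference lies inside the margin: at the listed levels, about 7–11% of the time at 25% against 20%, and 18–26% at 28% against 20%.
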